5.2.3.2 Dose Reduction Guidelines

Rovalpituzumab tesirine dose reduction for specific toxicities should occur as outlined in Table 5-1 and Table 5-2. If toxicities persist despite dose reduction, the dose should be discontinued. Exceptions to the dose modification guidelines may be permitted with written or electronic approval from the Medical Monitor. If a dose is reduced during the previous cycle, the reduced dose will be administered on Day 1 of subsequent cycles.

Table 5-1 Dose Reductions for Rovalpituzumab Tesirine

Starting Dose	First Dose Reduction (reduce dose)	Second Dose Reduction (discontinue dose)
0.3 mg/kg	0.2 mg/kg	Discontinue dosing

Table 5-2 Unacceptable Toxicities Requiring Dose Reduction

Toxicity	Grade ^a / Details
Thrombocytopenia	Grade 4 thrombocytopenia (or Grade 3 thrombocytopenia with bleeding) lasting more than 7 days and/or requiring platelet transfusion
Thrombocytopenia with bleeding	
Neutropenia	Grade 4 neutropenia lasting more than 7 days and/or requiring hematopoietic growth factor rescue, or any febrile neutropenia (Grade 3 or 4 neutropenia with concurrent fever $\geq 38.3^{\circ}\text{C}$)
Febrile neutropenia	
Laboratory abnormality	Grade 2 or higher hypoalbuminemia (in subject with normal baseline albumin levels) Grade 3 or 4 non-albumin laboratory abnormality considered clinically significant and treatment-related
Nonlaboratory toxicity	Grade 3 or 4 nonlaboratory toxicity (including infusion reactions) with the exception of fatigue, asthenia, nausea, or other manageable constitutional symptom
Skin toxicity	Grade 3 or higher cutaneous toxicity or symptom of photosensitivity (refer to Section 5.5.2)
Serosal effusions	Serosal effusions including: Grade 3 or higher pericardial effusion Grade 2 or higher pleural effusion Grade 3 or higher peripheral edema

a) Refer to Appendix 12.5 for definitions of NCI-CTCAE severity grades.

For the purposes of dose reduction, unacceptable toxicity is defined in Table 5-2. If unacceptable toxicity is encountered in Cycle 1, the Cycle 2 dose may be reduced (Table 5-1). If unacceptable toxicity is encountered at the reduced dose level, treatment should be discontinued. If the rovalpituzumab tesirine dose is reduced, the reduced dose level will be used for any subsequent cycles (i.e., retreatment).

Treatment guidelines for hematologic toxicities, and recommended actions regarding rovalpituzumab tesirine dosing, are outlined in Table 5-3.

Table 5-3 Guidelines for Hematologic Toxicities

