7.6.1.7 Potential Drug-Induced Liver Injury

Wherever possible, timely confirmation of initial liver-related laboratory abnormalities should occur prior to reporting a potential drug-induced liver injury (DILI) event ([FDA 2009](#)). All occurrences of potential DILIs, meeting the defined criteria, must be reported as SAEs.

Potential drug-induced liver injury is defined as:

- ALT or AST elevation > 3 times (3X) upper limit of normal (ULN); AND
- Total bilirubin > 2X ULN, without initial findings of cholestasis (elevated serum alkaline phosphatase), AND
- No other immediately apparent possible causes of aminotransferase (AT) elevation and hyperbilirubinemia, including, but not limited to, viral hepatitis, pre-existing chronic or acute liver disease or tumor(s), or the administration of other drug(s) known to be hepatotoxic

In general, an increase of serum AT to > 3X ULN should be followed by repeat testing within 48-72 hours of all four of the usual serum measures (ALT, AST, alkaline phosphatase, and total bilirubin) to confirm the abnormalities and to determine if they are increasing or decreasing.

Inquiry regarding symptoms should also be made (e.g., fatigue, nausea, vomiting, right upper quadrant pain or tenderness, fever, rash). Subjects may be retested locally, but normal laboratory ranges should be recorded and results made available to the investigator immediately for review. All data must be recorded on the case report forms. Close observation should be initiated if symptoms persist or repeat testing shows AT >3xULN for subjects with normal baseline

measures or 2-fold increases above baseline values for subjects with elevated values before drug exposure. If close monitoring is not possible, study drug should be discontinued.

Close observation includes:

- Repeating liver enzyme and serum bilirubin tests two or three times weekly. Frequency of retesting can decrease to once a week or less if abnormalities stabilize or the study drug has been discontinued and the subject is asymptomatic.
- Obtaining a more detailed history of symptoms and prior or concurrent diseases.
- Obtaining a history of concomitant drug use (including non-prescription medications and herbal and dietary supplement preparations), alcohol use, recreational drug use, and special diets.
- Ruling out acute viral hepatitis types A, B, C, D, and E; autoimmune or alcoholic hepatitis; NASH; hypoxic/ischemic hepatopathy; and biliary tract disease.

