- Obtaining a history of exposure to environmental chemical agents.
- Obtaining additional tests to evaluate liver function, as appropriate (e.g., INR, direct bilirubin).
- Considering gastroenterology or hepatology consultations.

Discontinuation of study drug should be considered if potential DILI is suspected and:

- ALT or AST $> 8x$ ULN
- ALT or AST $> 5x$ ULN for more than 2 weeks
- ALT or AST $> 3x$ ULN and (TBL $> 3x$ ULN or INR > 1.5)
- ALT or AST $> 3x$ ULN with the appearance of fatigue, nausea, vomiting, right upper quadrant pain or tenderness, fever, rash, and/or eosinophilia

All trial subjects showing possible DILI should be followed until all abnormalities return to normal or to the baseline state. Retreatment of subjects who develop possible DILI and have previously discontinued study drug may only be permitted upon approval by the sponsor and medical monitor.

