7.7.2 Laboratory Tests

Clinical laboratory assessments for this study include: hematology, blood chemistry and liver function tests (LFT). Most hematology, blood chemistry and LFT parameters will be graded according to NCI-CTCAE version 4.03, as applicable. Numeric values will be analyzed after conversion into standard international units, where applicable. A complete listing of all laboratory parameters with normal ranges in standard international units is included in Appendix 5. Laboratory values with grade 3 or above will be listed. For subjects with grade 3 or higher values, all values of that lab test will be listed.

Continuous clinical laboratory results will be summarized by analyte and by visit after conversion into standardized SI results. Summary statistics for the change from baseline to end-of-treatment (EOT), where end-of-treatment will be summarized using the last non-missing post-baseline result no more than 45 days after treatment discontinuation or initiation of subsequent therapy (whichever is first, if applicable), will be tabulated. The largest change from baseline (increase or decrease) will be summarized in a shift table based on the CTCAE grade which will include both scheduled and unscheduled visits.

Laboratory-based summaries will be provided as follows:

- Observed, change from baseline, and percent change from baseline at each scheduled visit and EOT in parameter results

- Shift from baseline to maximum post-baseline CTCAE grade for hematology laboratory results
- Shift from baseline to maximum post-baseline CTCAE grade for chemistry laboratory results
- Elevations in AST, ALT, total bilirubin, and alkaline phosphatase as outlined in the FDA Guidance for Industry pertaining to premarketing clinical evaluations for drug-induced liver injury (DILI):
 - Elevations of AST, ALT, and either ALT or AST: 3x-, 5x-, 10x-, and 20xULN
 - Elevations of bilirubin defined as total bilirubin >2 xULN
 - Elevations of alkaline phosphatase >1.5 xULN
 - Elevations of ALT or AST (>3 xULN) accompanied by elevated total bilirubin (>1.5 xULN, >2 xULN)

In addition, a listing of potential Hy's Law cases (i.e., subjects with AST or ALT >3 xULN in combination with bilirubin >2 xULN) will be also presented. Results from unscheduled or repeated assessments will be included in the DILI evaluations, with elevations of AST or ALT in combination with total bilirubin at the same unscheduled or repeat assessment.

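### A liver case that meets the protocol's own potential-DILI definition can meet none of the four discontinuation items, because the list's bilirubin cut-off is 3x ULN and the definition's is 2x ULN

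*Protocol*

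**What the plan says.** All the rules that matter are in Protocol Section 7.6.1.7.

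- **Definition.** Potential DILI needs three things: ALT or AST above 3x ULN; "Total bilirubin > 2X ULN, without initial findings of cholestasis (elevated serum alkaline phosphatase), AND" no other immediately apparent cause.
- **Reporting.** "All occurrences of potential DILIs, meeting the defined criteria, must be reported as SAEs".
- **Monitoring.** Confirmed aminotransferase rises lead to close observation, with liver enzymes and bilirubin repeated two or three times weekly. "If close monitoring is not possible, study drug should be discontinued".
- **Discontinuation list.** The lead-in is "Discontinuation of study drug should be considered if potential DILI is suspected and", followed by four items: (1) ALT/AST above 8x ULN; (2) above 5x ULN for more than 2 weeks; (3) above 3x ULN together with "TBL $> 3x$ ULN or INR > 1.5"; (4) above 3x ULN with one of several named symptoms or eosinophilia.
- **Afterwards.** "Retreatment of subjects who develop possible DILI and have previously discontinued study drug may only be permitted upon approval" by the sponsor and medical monitor.

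SAP Section 7.7.2 lists potential Hy's Law cases as "subjects with AST or ALT >3 xULN in combination with bilirubin >2 xULN". Neither document explains the 3x bilirubin figure in item 3.

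**The concern.** The definition marks the combined aminotransferase and bilirubin rise as serious enough for mandatory SAE reporting. One would expect that same finding to prompt the investigator to consider stopping the drug. As written it need not, because the bilirubin threshold rises from 2x to 3x between the definition and the list.

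Items 1, 2 and 4 and the INR limb of item 3 do not mention bilirubin. If *suspected* is read loosely, ALT just above 3x with fatigue and normal bilirubin prompts consideration of stopping, while an asymptomatic subject who meets the full definition does not.

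The INR limb is not a dependable substitute. Coagulation tests are scheduled at screening, Day 1 and end of treatment (Sections 6.2, 6.3.2, 6.4), not at Day 15 or Day 29 (6.3.6, 6.3.8), and under close observation INR is done only as appropriate. Bilirubin is in every chemistry panel (7.6.4), so the limb most often available is the one with the mismatched cut-off.

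At stake is whether one more dose of the initial course, or a later retreatment, goes ahead without a liver-specific prompt to reconsider.

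**Working it through.** There is no sample size, power or error rate to reproduce. The check is logical: write the definition and the four items as rules and find the profiles that meet the first and none of the second.

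**Inputs (Protocol 7.6.1.7), as multiples of ULN, with cholestasis and other causes taken as absent**

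- Definition: AT > 3 and TBL > 2, where AT is ALT or AST
- Item 1: AT > 8
- Item 2: AT > 5 for more than 2 weeks
- Item 3: AT > 3 and (TBL > 3 or INR > 1.5)
- Item 4: AT > 3 and a listed symptom or eosinophilia

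**Solving for the gap.** Definition met and every item failed requires:

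- from the definition, AT > 3 and TBL > 2;
- from item 1, AT ≤ 8;
- from item 2, AT not above 5 for more than 2 weeks;
- from item 3, given AT > 3, TBL ≤ 3 and INR ≤ 1.5;
- from item 4, given AT > 3, no listed symptom or eosinophilia.

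So the gap is AT above 3x and up to 5x at any duration, or above 5x and up to 8x for no more than 2 weeks, with TBL above 2x and up to 3x, INR at most 1.5 and no symptoms. It is there whether *suspected* means the full definition or something looser, because the items themselves fail.

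**Worked cases (INR 1.2, no listed symptom; all meet the definition)**

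| AT | TBL | AT > 5x for > 2 weeks | Items met now | Items met with TBL > 2x in item 3 |
|---|---|---|---|---|
| 4x | 2.5x | no | none | 3 |
| 7x | 2.5x | no | none | 3 |
| 7x | 2.5x | yes | 2 | 2 and 3 |
| 4x | 3.5x | no | 3 | 3 |

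**Grid check.** AT {2.5, 3.5, 5.5, 8.5}, TBL {1.5, 2.01, 2.5, 3.0, 3.01}, INR {1.2, 1.6}, symptoms yes/no, and duration above 2 weeks yes/no where AT > 5. Definition-meeting profiles: 5 AT-by-duration combinations × 4 TBL values × 2 × 2 = 80. With no item met at the 3x cut-off: 2 AT values × 3 TBL values = 6 of 80. At a 2x cut-off: 0 of 80. These are grid cells, not patient frequencies.

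**Why 2x closes the gap.** The bilirubin limb of item 3 becomes AT > 3 and TBL > 2, which are the definition's own laboratory limits. Any case meeting the definition then meets item 3.

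**The case against.** The strongest defence is that 3x is a deliberate second tier: the definition leads to SAE reporting and close observation, and only a worse picture leads to considering a stop. If *suspected* means the full definition is met, a 2x cut-off makes item 3 fire for every such case and the other items become redundant. That stands as a cost of the change, and deliberate intent cannot be ruled out. But the documents do not state it, and the tiers are not graded consistently. Even on that strict reading, AT 3.1x with TBL 2.1x and fatigue meets item 4, while AT 7.9x for up to 2 weeks with TBL 3.0x, INR at most 1.5 and no symptoms meets nothing.

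The second defence is that the practical effect is small, and most of it stands:

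- The list only asks that stopping be considered.
- The case is an SAE reportable within 24 hours with causality (7.6.1.4) and is closely observed.
- The next dose waits until clinically significant AEs return to Grade 0 or 1 or baseline (5.2.2, 5.2.3.1).
- The investigator may stop for an AE or by decision (4.3.1).
- The initial course is two doses, so after Cycle 1 only one is left.
- Retreatment requires that the first two doses were tolerated (3.1) and that all entry criteria are met again (Section 4), including the bilirubin and aminotransferase limits in 4.1.
- Fatigue and nausea are among the most frequent AEs (1.1.3), so item 4 will catch some of these subjects.

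None of these is itself a liver-specific prompt to consider stopping. The instruction to stop when close monitoring is impossible does not apply when it is possible, and the retreatment approval sentence covers only subjects who have already discontinued.

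A reader might also infer that the protocol conflicts with the SAP. It does not: the Hy's Law listing is a descriptive output, omits the protocol's cholestasis and other-cause exclusions, and need not match a dosing rule. It is context only.

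**Conclusion.** The mismatch is real and internal to Section 7.6.1.7. A bounded set of subjects meets the protocol's SAE-level definition of potential DILI and none of the four items that prompt consideration of discontinuation. The result assumes no cholestasis and no other apparent cause, as the definition requires. The suggestion is worth considering; it is not a serious defect.

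Three stronger readings are not supported:

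- **That these subjects are unprotected.** Reporting, close observation, recovery before redosing and investigator discretion all apply.
- **That they would receive Cycle 2 at full dose.** Table 5-2 lists for dose reduction a "Grade 3 or 4 non-albumin laboratory abnormality considered clinically significant and treatment-related". Whether part of the gap reaches Grade 3 depends on CTCAE liver rows that Appendix 12.5 does not reprint, so the documents do not settle it.
- **That 3x is a drafting error.** The documents do not explain the figure either way.

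The documents give no rate of potential DILI, so no expected number of affected subjects can be stated. No efficacy analysis is touched.

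**What to change.** In Protocol Section 7.6.1.7, change item 3 to: *ALT or AST > 3x ULN and (TBL > 2x ULN or INR > 1.5)*. Leave the lead-in, the other three items and the SAE definition as they are.

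Do not add a separate, higher cut-off for Gilbert's disease. The definition has no such exception, so adding one to item 3 would reopen the gap for any Gilbert's subject who meets the definition. The other-causes clause and the advisory wording already leave room for judgement in those subjects.

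The cost is one threshold in a protocol amendment with IRB/IEC approval. Bilirubin is already in every chemistry panel, so nothing new is collected. A few more subjects will prompt consideration of stopping, and on the strict reading of the lead-in the remaining items become redundant. If the sponsor did intend 3x as a second tier, the alternative is to say so in the section and give the reason.

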7.6.2 Physical Examination

Physical examinations will include assessments of the head and neck, heart, lungs, abdomen, extremities, neurological and skin.

7.6.3 Vital Signs, Weight and Height

Vital signs will include heart rate, respirations, blood pressure, temperature, and weight. All vital signs should be measured after the subject has been sitting/resting for at least 5 minutes. Weight will be measured at the times indicated. For adult subjects, measurements of height obtained within the prior 6 months may be utilized.

In the event of an infusion reaction or hypersensitivity reaction, vital signs should be monitored more frequently than originally scheduled and as clinically indicated.

7.6.4 Clinical Laboratory Tests

Laboratory assessments will be performed to evaluate safety at scheduled time points (see Appendix 12.1) during the course of the study. The following assessments will be performed at the local laboratory:

- Complete Blood Count, including white blood cell count with five-part differential (neutrophils, lymphocytes, monocytes, eosinophils, and basophils), red blood cell count, platelet count, hemoglobin, and hematocrit.
- Chemistry panel, including electrolytes (sodium, potassium, chloride, and carbon dioxide), creatinine, blood urea nitrogen (BUN), estimated glomerular filtration rate, glucose, albumin, total protein, liver function tests (total and direct bilirubin, ALT, AST, alkaline phosphatase, lactate dehydrogenase), amylase, and lipase.
- Coagulation tests, including prothrombin time (PT), partial thromboplastin time (PTT), and international normalized ratio (INR).
- Urinalysis, including dipstick results for color, appearance, specific gravity, pH, glucose, bilirubin, ketones, occult blood, and protein; as well as spot protein and creatinine.
- Hepatitis B and C tests include Hep B surface antigen (HBsAg), Hep B surface antibody (HBsAb), Hep B core antibody (HBcAb) and hepatitis C virus (HCV) antibody. Results that may be consistent with chronic or active infection, and/or subjects with known prior active hepatitis B or C infection, should undergo PCR tests for Hep B and/or C, respectively.
- Pregnancy test, consisting of blood or urine testing for beta-human chorionic gonadotropin (β -hCG).

7.6.5 Electrocardiograms

Throughout the study, subjects will be monitored for changes in cardiac conduction through ECGs (Appendix 12.1). ECGs consist of 12-lead studies, performed within a 5 minute window after at least 10 minutes of quiet rest in a supine position.

7.6.6 Echocardiogram

Echocardiograms will be performed at the indicated times to assess any pericardial effusions, if present, as well as cardiac function (left ventricular ejection fraction, LVEF).

7.6.7 ECOG Performance Status

ECOG performance Status (Appendix 12.2) will be evaluated at protocol-specific time points (Appendix 12.1).

7.6.8 Fluid Retention Questionnaire

Throughout the treatment period, subjects will be asked about the development of any new or worsening peripheral edema or dyspnea (Appendix 12.7). This assessment may take place virtually (e.g. by telephone).

7.6.9 Daily Weight Diary

Throughout the treatment period, subjects will maintain a diary of daily weights.

7.7 Appropriateness of Measurements

The safety measures that will be used in this trial are considered standard procedures for evaluating the potential adverse effects of study medications. Adverse events and, when applicable, clinical laboratory data will be graded using NCI CTCAE, version 4.03.

Response will be assessed according to RECIST v1.1 (Eisenhauer 2009), which includes standard criteria for evaluating response in solid tumors. The intervals of evaluation in this protocol are appropriate for disease management.

Standard tests will be performed to detect the possible presence of specific antibodies to study drug. Pharmacokinetic assessments for drug activity are also common in clinical studies.

8 DATA QUALITY CONTROL AND QUALITY ASSURANCE

8.1 Site Training and Monitoring Procedures

A study manual with instructions for study compliance and CRF completion will be provided. Prior to the enrollment of subjects at the site, the sponsor or its designated clinical and medical personnel will review the following items with the investigator and clinic staff:

- The protocol, study objectives, eligibility requirements, study procedures, registration and withdrawal processes
- Current Investigator's brochure/package insert
- Recording and reporting AEs and SAEs
- Enrollment goals and study timelines
- The CRF completion process and source documentation requirements
- Monitoring requirements
- Institutional Review Board/Independent Ethics Committee (IRB/IEC) review and approval process
- Informed consent process
- Good Clinical Practice guidelines and related regulatory documentation requirements
- Key study team roles and responsibilities
- Investigational product storage, accountability, labeling, dispensing and record keeping
- Subject coding
- Study samples/specimen collection, handling and shipping
- Protocol compliance
- Clinical study record keeping, document retention, and administrative requirements

Monitoring visits will occur periodically, with frequency dependent on the rate of enrollment and workload at each site. During monitoring visits, the sponsor representative will review regulatory documentation, CRFs, source documentation, investigational product storage, preparation, and accountability. The CRFs will be reviewed for completeness, adherence to the provided guidelines, and accuracy compared to the source documents. The investigators must ensure that the monitor is allowed to inspect all source documents pertinent to study subjects, and must

cooperate with the monitor to ensure that any problems noted in the course of the trial are resolved. The investigator must maintain a comprehensive and centralized filing system of all study-related documentation that is suitable for inspection by the sponsor or its designated monitors and by quality assurance auditors, or representatives of regulatory authorities.

8.2 Data Management Procedures

AbbVie or its designee will provide CRF Completion Guidelines for electronic CRF (eCRF) data entry. Study specific data management procedures will be maintained in the data management plan. Queries resulting from edit checks and/or data verification procedures will be posted electronically in the eCRF.

8.3 Access to Source Data

The investigator will permit the sponsor's representatives to monitor the study as frequently as the sponsor deems necessary to determine that protocol adherence and data recording are satisfactory. Appropriate measures to protect subject confidentiality are to be employed during monitoring. The CRFs and related source documents will be reviewed in detail by the monitor at each site visit. Original source documents or certified copies must be provided to the sponsor for review. This review includes inspection of data acquired as a requirement for participation in this study and other medical records as required to confirm that the information contained in the CRFs, such as disease assessments, AEs, and concomitant therapies, is complete and correct. Other study records, such as correspondence with the sponsor and the IRB/IEC and screening and drug accountability logs will also be inspected. All source data and study records must also be available for inspection by representatives of regulatory authorities.

